8.2 VISIT 2: TREATMENT PERIOD (DAY 1)

For each cohort, subjects approved by the EAC for further participation in the study will return to the clinic within 28 days of the screening visit on the morning of Day 1, in the practically defined OFF state (having not taken any anti-PD medications since 10 PM the evening before).

Subjects will come to clinic in a fasted state and will be administered a standard low protein breakfast. Subjects will be randomized to either BTRX-246040 or placebo.

In the clinic, subjects determined to be in the OFF state by the Investigator will be dosed with study drug and UPDRS Part III motor response and dyskinesia rating, and ON/OFF status will be assessed pre-dose and every 30 minutes post-dose for 4 hours, and then hourly for an additional 4 hours (i.e., 8 hours total post-dose). Time to ON and duration of ON, if applicable, will also be recorded.

Subjects who reach and remain in the ON state for 8 hours may resume their regularly scheduled anti-parkinsonian medications 8 hours post-dosing. Subjects should remain on study drug until they experience an OFF episode after a full ON for 8 hours. However, if after 4 hours post study drug dosing, a subject's motor symptoms are severe and not responsive to study drug, the subject's regularly scheduled levodopa dose and other anti-parkinsonian medications may be administered, if deemed necessary based on the judgment of the investigator. All subjects whether they are administered their regularly scheduled anti-parkinsonian medications or not, will continue with study procedures until the end of the observation period of 8 hours.

The following assessments will be completed on Day 1 - see the Schedule of Assessments ([Appendix 1](#)) for details:

1. Collection of concomitant medications

2. Vital Signs: (BP and pulse both supine and standing, respiratory rate, temperature) and weight. Three sets each of supine and standing BP and pulse rate will be measured at least 15-20 minutes apart at pre-dose and will be measured once at 2, 4, 6, and 8 hours after dosing
3. C-SSRS – since last visit version
4. QUIP-RS – since last visit version
5. 12-lead ECG pre-dose and 1 hour after study drug administration.
6. Randomization via IWRS
7. UPDRS Part III and dyskinesia rating in the OFF state pre-dose and every 30 minutes for 4 hours and then hourly for another 4 hours (i.e., 8 hours following study drug administration). If the subject remains ON after 8 hours, they should be called the next morning to record the time they turned OFF, and the time they took their first regularly scheduled anti-parkinsonian medications after study drug, to a maximum of 24 hours.
8. Administration of Study drug
9. Time to ON and duration of ON following study drug administration.

11. Drug accountability.

12. Collection of AEs.

Subjects will be discharged from the clinic and instructed to return to the clinic 7 days later (Day 8 ±1).

8.3 VISIT 3: SAFETY FOLLOW-UP (DAY 8 ±1)

All randomized subjects will return to the clinic for a final safety visit approximately 7 days after the last dose of study drug.

The following assessments will be performed at the follow-up visit (see Schedule of Assessments [Appendix 1] for details):

1. Collection of concomitant medications.
2. Vital signs (BP and pulse both supine and standing, respiratory rate, temperature), and weight
3. C-SSRS – since last visit version
4. QUIP-RS since last visit version
5. Physical and neurological examinations
6. 12-lead ECG
7. Safety laboratory assessment (including clinical chemistry panel, hematology, coagulation [including PT, aPTT, INR] parameters and urinalysis)

8. Collection of AEs.

8.4 EARLY TERMINATION VISIT

If the participant is willing, all of the procedures scheduled to be performed on the Day 8 visit should be conducted at the early termination visit (see Schedule of Assessments [[Appendix 1](#)]).

9 TREATMENT

9.1 TREATMENTS ADMINISTERED

This study involves a comparison of BTRX-246040 versus placebo taken orally as a single dose in 3 sequential ascending dose cohorts of 8 subjects each with a 6:2 randomization to BTRX-246040 or placebo. The planned dosing for each cohort will be as noted in Table 1. Following completion of the first cohort, unblinded safety, tolerability, efficacy and, if available, PK data will be reviewed by an unblinded Dosing Review Committee (DRC) to determine if it is safe to proceed to the next higher dose level (see [section 9.7](#)). Similar dosing review and determination of dosing for each subsequent cohort will be performed based on all data available from previous cohorts. At any point, the DRC may request that a dosage be repeated rather than increased.

Table 1 Treatment Regimens

Treatment Group	Regimen*
BTRX-246040	
• Cohort 1 - 40 mg (██████)• Cohort 2 - 80 mg (██████)• Cohort 3 - 120 mg (██████)
Placebo	
• Cohort 1 - (██████)• Cohort 2 - (██████)• Cohort 3 - (██████)

9.2 MATERIALS AND SUPPLIES

BTRX-246040 and placebo capsules and packaging will be identical to maintain Investigator and subject blinding. Subjects should be instructed to swallow capsules whole and not crush or chew and store the capsules in their original packaging at the temperature listed on the package label. Clinical trial materials will be labeled according to the regulatory requirements.

9.3 METHOD OF ASSIGNMENT TO TREATMENT

Subjects who meet all inclusion criteria and are subsequently not excluded by the exclusion criteria will be randomized to double-blind treatment at Visit 2 using an IWRS. Subjects will be randomized in a 6:2 ratio to one of two treatment arms (BTRX-246040 or placebo).

9.4 RATIONALE FOR SELECTION OF DOSES IN THE STUDY

The starting dose for cohort 1 will be 40 mg. A

[REDACTED]

Another Phase 2 study, NEP-MDD-201, compared single-daily dosing of BTRX-246040 vs. placebo administered over 8 weeks in a double-blind, placebo-controlled, parallel-group study. After screening, eligible subjects were randomized to either 40 mg of BTRX-246040 or placebo and after one week the dose was increased to 80 mg and allowed to be down-titrated to 40 mg at the next visit for tolerability. BTRX-246040 and placebo had a similar rate of dose reduction (3/53 [5.7%] vs. 2/51 [3.9%]). The most common TEAEs that occurred more frequently with BTRX-246040 than placebo were nausea (5/53 [9.4%] vs. 3/51 [5.9%]), upper respiratory tract infection (3/53 [5.7%] vs. 2/51 [3.9%]), gastroenteritis, urinary tract infection, anxiety, and irritability (all 3/53 [5.7%] vs. 1/51 [2.0%]). One subject assigned to the placebo group had an SAE (Preferred Term: rhabdomyolysis). No deaths were reported.

In all three Phase 2 studies, most TEAEs were mild or moderate in severity. There were no notable treatment-related clinical laboratory findings or abnormal ECGs. Vital signs were generally within normal ranges, with no notable treatment-related changes reported following 40 mg and following 80 mg QD BTRX-246040. In all studies, no increase in suicidal ideation or behavior relative to placebo was detected following BTRX-246040 administration, as assessed by the C-SSRS.

[REDACTED]

As BTRX-246040 has not previously been tested in PD, three dosing cohorts (40, 80, and 120 mg) of 8 subjects with a 6:2 randomization to BTRX-246040 or placebo are planned in order to explore the effective dose range.

9.5 SELECTION AND TIMING OF DOSES

BTRX-246040 has only been dosed with a light breakfast in clinical pharmacology studies to date; there are currently no PK data available for BTRX-246040 when dosed in the fasted state.

Therefore, in the current study, subjects will take the investigational study drug orally in the morning with a light breakfast.

9.6 BLINDING

This is a double-blind study. Subjects, site personnel, and the Sponsor will be blinded to treatment.

The Investigator should make every effort to contact the medical monitor prior to unblinding a subject's treatment assignment. If an Investigator, site personnel performing the assessments, or subject is unblinded, the subject must be discontinued from the study. In cases where there are ethical reasons to have the subject remain in the study, the Investigator must obtain specific approval from the Sponsor-designated Medical Monitor for the subject to continue in the study.

9.7 DOSING REVIEW COMMITTEE

Safety will be evaluated by the DRC, which will be comprised of the Principal Investigator, Medical Monitor and Pharmacovigilance to assess safety, tolerability, and efficacy of BTRX-246040. The DRC may make the following decisions based on its review of the available data:

- escalation to the next higher dose level
- escalation of the dose level is not warranted because of dose-related toxicity
- escalation is warranted to a lower dose than originally planned
- escalation should be postponed pending collection of additional data from currently-enrolled subjects
- additional subjects should be added to a cohort to better understand safety at that level.

After enrollment of the first cohort has been completed, doses for subsequent cohorts may be modified as above based on review of the available data (safety, tolerability, efficacy, and PK) by an unblinded Dosing Review Committee (DRC). A similar review and determination of dosing for the subsequent cohort will be performed after completion of cohorts 1 and 2 and based on all data available from previous cohorts.

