Following signing of IRB-approved informed consent, screening, and acceptance by an Enrollment Authorization Committee, subjects in each cohort who meet entry criteria will present to the clinic on the morning of Day 1 in the practically defined OFF state (having withheld anti-parkinsonian medications after 10:00 PM the evening prior). Prior to dosing on Day 1, Subjects will be randomized to either placebo or BTRX-246040. Subjects will then be dosed with study drug and UPDRS Part III motor response, dyskinesia rating and ON/OFF status will be assessed pre-dose and every 30 minutes for 4 hours and then hourly for 4 additional hours (i.e., 8 hours total post-dose). Subjects who turn ON following study drug administration, and remain ON after 8 hours, should be called the next morning to record the time they turned OFF and took their first regularly scheduled anti-parkinsonian medications after study drug, to a maximum of 24 hours.

On Day 1 subjects will come to clinic in a fasted state and will be administered a standard low protein breakfast. [REDACTED]

Subjects who reach and remain in the ON state for 8 hours will resume their regularly scheduled anti-parkinsonian medications 8 hours post-dosing. Subjects should remain on study drug until they experience an OFF episode after a full ON for 8 hours. However, if after 4 hours post study drug dosing, a subject's motor symptoms are severe and not responsive to study drug, the subject's regularly scheduled levodopa dose and other anti-parkinsonian medications may be administered, if deemed necessary based on the judgment of the investigator. All subjects, whether they are administered their regularly scheduled anti-parkinsonian medication or not will continue with study procedures until the end of the observation period of 8 hours. Orthostatic vital signs will be assessed pre-dose and 2, 4, 6, and 8 hours after dosing.

Subjects will return to the clinic 7 days later (Day 8) for a follow-up safety visit.

Following completion of cohorts 1 and 2, a Dosing Review Committee (DRC) meeting will take place to review available unblinded safety, tolerability, efficacy and, if available, PK data and determine if it is safe to go up to the next higher dosage for the next cohort. At any point, the DRC can request that a dosage be repeated for safety or tolerability rather than increased.

Inclusion Criteria

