reach and remain in the ON state for 8 hours may resume their regularly scheduled anti-parkinsonian medications 8 hours post-dosing. Subjects should remain on study drug until they experience an OFF episode after a full ON for 8 hours. However, if after 4 hours post study drug dosing, a subject's motor symptoms are severe and not responsive to study drug, the subject's regularly scheduled levodopa dose and other anti-parkinsonian medications may be administered, if deemed necessary based on the judgment of the investigator. All subjects, whether they are administered their regularly scheduled anti-parkinson medication or not will continue with study procedures until the end of the observation period of 8 hours.

Subjects will come to clinic in a fasted state and will be administered a standard low protein breakfast.

Orthostatic vital signs will be assessed pre-dose and 2, 4, 6, and 8 hours after dosing.

Subjects will return to the clinic 7 days later (Day 8) for a follow-up safety visit.

Following completion of cohorts 1 and 2, a Dosing Review Committee (DRC) meeting will take place to review available unblinded safety, tolerability, efficacy and, if available, PK data and determine if it is safe to go up to the next higher dosage for the next cohort. At any point the DRC can request that a dosage be repeated.

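### The Principal Investigator sits on the unblinded Dosing Review Committee, although the protocol blinds site personnel and relies on blinded Investigators

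*Protocol*

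**What the plan says.** Protocol 9.7 sets the membership of the Dosing Review Committee (DRC): "Safety will be evaluated by the DRC, which will be comprised of the Principal Investigator, Medical Monitor and Pharmacovigilance". Later in the same section, doses may be changed "based on review of the available data (safety, tolerability, efficacy, and PK) by an unblinded Dosing Review Committee (DRC".

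The Synopsis gives the timing: "Following completion of cohorts 1 and 2, a Dosing Review Committee (DRC) meeting will take place". Section 6.1 gives the content: "a Dosing Review Committee (DRC) meeting will take place to review available unblinded safety, tolerability, efficacy and, if available, PK data". Section 9.1 agrees: "unblinded safety, tolerability, efficacy and, if available, PK data will be reviewed by an unblinded Dosing Review Committee (DRC". Section 10.5.8 also describes an unblinded review after cohorts 1 and 2, but mentions only safety and tolerability. Among the decisions open to the DRC, 9.7 lists that "additional subjects should be added to a cohort to better understand safety at that level".

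On the blind, 9.6 says: "Subjects, site personnel, and the Sponsor will be blinded to treatment". It goes on: "If an Investigator, site personnel performing the assessments, or subject is unblinded, the subject must be discontinued from the study". Its one relief lets such a subject stay for ethical reasons with the Medical Monitor's approval. Section 6.2 credits the blinding of both Investigators and subjects with controlling expectation bias.

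**The concern.** A site role that 9.6 blinds is made a member of a committee that sees unblinded data, and the protocol provides neither an exception nor a firewall.

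The primary endpoint is the maximal change in UPDRS Part III, which a rater scores. The Investigator decides on Day 1 whether a subject is OFF before dosing (8.2). From 4 hours after dosing, the Investigator also judges whether regular anti-parkinsonian medication is given while assessments continue to 8 hours. Sections 10.2.2.1 and 10.2.2.2 assign AE severity and causality to the Investigator, and those AE data feed the next escalation decision.

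Someone who has already seen unblinded results from a lower dose could do all of this in the next cohort, or in subjects added to a cohort already reviewed. That is the expectation bias that 6.2 says the design controls.

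**Working it through.** **Passages side by side**

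| Place | What it fixes for the Principal Investigator |
|---|---|
| 9.7 | Member of the DRC; the DRC is unblinded |
| Synopsis, 6.1, 9.1 | The DRC sees unblinded safety, tolerability and efficacy data |
| 13.3.2 | The title is a site role: every principal Investigator signs the protocol |
| 9.6 | Site personnel are blinded; no exception for the DRC |
| 6.2 | Investigators are blinded, and this controls expectation bias |

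The first three rows make this person an unblinded member of site personnel. The last two say there is none. No other section exempts DRC members or bars the DRC Investigator from assessing subjects.

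**Other DRC members.** Section 10.5.8 has the Medical Monitor follow blinded safety data throughout, while 9.7 puts that role on the unblinded DRC. This is unclear rather than plainly contradictory. Whether the Sponsor blind in 9.6 covers a Sponsor-designated monitor, or Pharmacovigilance, is an inference.

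**What the DRC Investigator has seen** (3 cohorts of 8, randomized 6:2)

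- Before cohort 2: 8 subjects (6 drug, 2 placebo).
- Before cohort 3: 2 × 8 = 16 subjects (12 drug, 4 placebo).

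**What that person could then assess**

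- Subjects dosed after the first review: 8 + 8 = 16 of 24 = 67%.
- Day 1 ratings per subject (8.2): 1 pre-dose + 8 half-hourly over 4 hours + 4 hourly = 13.
- All planned ratings: 24 × 13 = 312.
- Ratings after the first review: 16 × 13 = 208, that is 8 × 13 = 104 after each review.

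The exposed share is therefore 0 to 16 subjects and 0 to 208 ratings, plus added subjects, whose number is not fixed. The rating counts are maxima, because footnote 5 of Appendix 1 lets ratings stop once a subject turns OFF. The protocol does not locate the true value in this range: 9.7 names one Principal Investigator, whereas 13.2 and 13.3.2 allow several sites.

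**Subjects in a cohort already reviewed.** Day 1 ratings are finished if review follows cohort completion. Late safety may still be open. SAEs are collected for 30 days after the dose (10.2.5), and the Day 8 (±1) visit falls 7 (±1) days after it. Collection thus continues for 30 − 7 = 23 days past that visit (22 to 24). This bears on the blind only if the DRC meets within that window and sees data by subject rather than by arm. The protocol states neither.

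**The case against.** The strongest reply is that the exception is implied. The protocol repeatedly calls the DRC unblinded and lists its members, and 10.5.8 sets blinded monitoring beside unblinded review. The specific rule can then be read as qualifying the general sentence in 9.6, so that only a cross-reference is missing. This would serve for a committee separate from the sites. It does not explain seating an Investigator on it while 6.2 counts on Investigators being blinded.

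Second, 6.2 speaks of blinding to assignment, dosing takes one day, and review follows cohort completion, so nobody rating a subject knows that subject's assignment. This largely stands and limits the risk to shifted expectations. It is not fully assured: the Synopsis, 6.1 and 9.7 also tie dose changes to completed enrollment of cohort 1, and 9.7 refers to subjects still enrolled.

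Third, nothing says the Principal Investigator does the UPDRS ratings. Sections 10 and 10.1.1 allow any qualified trained rater. That stands, and it is why the range starts at zero. The OFF judgement and the AE assessments are, however, given to the Investigator.

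Fourth, efficacy is descriptive with no formal comparison, and expectations shared by both arms leave the concurrent placebo contrast within a cohort largely intact. This also stands, and places the effect mainly on the informal comparison across doses.

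Finally, 10.5.8 omits efficacy from the DRC's review. The Synopsis, 6.1, 9.1 and 9.7 all include it.

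The discontinuation sentence in 9.6 reads as meant for individual code-breaks, not planned DRC review. The text should say so.

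**Conclusion.** The concern holds and should be fixed. As written, the double-blind stated in 6.2 and 9.6 is not one the design has for the Principal Investigator on the DRC. Confidence in that textual conflict is high.

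The possible reach is 0 to 67% of planned subjects, assuming planned cohort sizes and review only after cohorts 1 and 2. A repeated dose or added subjects would raise the count. The size of any resulting bias cannot be derived from the protocol. Concealed later allocations and a purely descriptive analysis keep the consequence moderate.

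**What to change.** Reconcile 6.2, 9.6, 9.7 and 10.5.8.

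- **9.6:** list which DRC members see unblinded data, settling the matter for the Medical Monitor and Pharmacovigilance. State that planned DRC review is not a code-break under the discontinuation sentence.
- **9.7:** adopt one of the two options below, and state whether the DRC sees data by subject or by arm.
- **6.2 and 10.5.8:** stop describing unblinded DRC members as blinded.

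**Option A (simpler).** The Investigator comments on blinded data and receives only the dose decision. The Medical Monitor and Pharmacovigilance remain as the unblinded members. The cost is wording, and less Investigator input to escalation. The Medical Monitor also advises on eligibility of later subjects (exclusion criteria 25 and 30), so 9.6 must acknowledge that this role is unblinded.

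**Option B.** An Investigator who sees unblinded DRC data does not rate UPDRS Part III, judge ON/OFF status or assess AEs in later or extended cohorts. Nor does that person assess SAEs still being collected in reviewed cohorts. Trained staff outside the DRC take over from screening, so that one rater follows each subject as 10.1.1 asks. Sections 8.2 and 10.2.2 then need a designee clause like the one in 8.1. The text must also name who makes the 4-hour judgement on regular medication, without changing its criterion. This option needs a physician outside the DRC at that site for AE causality. A site without one would have to use option A.

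Neither option adds subjects or visits, and trained raters are already required by section 10.

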9.8 CONCOMITANT THERAPIES

In general, stable doses of concomitant medications will be allowed during the study if stable dosing occurred during the 1 month prior to the screening visit. Subjects may receive antidepressant medications if the doses have been stable for at least 8 Weeks prior to the screening visit. The Investigator should instruct subjects to notify the study site about any new medications he/she takes and about any significant non-pharmacological therapies administered after the start of the study drug (e.g. acupuncture, hypnosis etc.). All medications, including over the counter medications and supplements, and also significant non-pharmacological therapies, administered after the subjects start treatment with study drug must be listed on the corresponding CRFs.

9.8.1 ANTI-PD MEDICATIONS

Subjects are required to be on a stable regimen of permitted anti-PD medications for at least 4 weeks (with the exception of MAO-B inhibitors, which must be stable for 8 weeks) prior to Screening (see inclusion and exclusion criteria Section 7.1 and 7.2). All efforts should be made to maintain subjects on the same stable dose and frequency of their anti PD medications throughout their participation. The addition of any new anti-PD medications or an increase in the dose of any anti-PD medications is not permitted. Likewise, changes to the frequency (number of doses taken per day) or to the intervals between doses (duration of time between doses on a given day) of a subject's anti-PD medication(s) are not permitted. An as needed dose of levodopa or other anti-PD medication would be considered a change in frequency as it is not a regular part of the daily regimen.

9.8.2 PROHIBITED MEDICATIONS/TREATMENTS

The following concomitant medications are prohibited:

- Current or previous use of Duopa/Dudopa
- Current use of Apomorphine
- All anti-psychotic medications for more than 1 month within the past 2 years, or any exposure within the past year
- Use of proton pump inhibitors within 5 half-lives of Visit 2
- Fluoxetine and irreversible monoamine oxidase inhibitors within 4 weeks of Visit 2
- Bupropion within 8 weeks of the screening visit
- Current use or use within 5 half-lives of Screening of any medications or supplements that are strong inhibitors or inducers of CYP3A4. Examples are provided below. A further listing of strong CYP3A4 inhibitors and inducers can be found in [Appendix 2](#).
 - Strong CYP3A4 inhibitors include:
 - Antifungal azoles
 - Macrolide antibiotics
 - Human immunodeficiency virus protease inhibitors
 - Boceprevir
 - Nefazodone
 - Conivaptan
 - Strong CYP3A4 inducers include:
 - Rifampin
 - Phenytoin
 - Carbamazepine
 - Enzalutamide
 - St. John's wort

